5.7.2.2 Treatment Schedule Adjustments

Adverse events (both non-serious and serious) associated with pembrolizumab exposure may represent an immunologic etiology. For assessment and management of irAEs, investigators should refer to the last version of pembrolizumab IB. These adverse events may occur shortly after the first dose or several months after the last dose of treatment. Pembrolizumab must be withheld for drug-related toxicities and severe or life-threatening AEs as per Table 1.

Table 1: Treatment schedule adjustments for pembrolizumab

General instructions:				

 1. Corticosteroid taper should be initiated upon AE improving to Grade 1 or less and continue to taper over at least 4 weeks. 2. For situations where pembrolizumab has been withheld, pembrolizumab can be resumed after AE has been reduced to Grade 1 or 0 and corticosteroid has been tapered. Pembrolizumab should be permanently discontinued if AE does not resolve within 12 weeks of last dose or corticosteroids cannot be reduced to ≤ 10 mg prednisone or equivalent per day within 12 weeks. 3. For severe and life-threatening irAEs, IV corticosteroid should be initiated first followed by oral steroid. Other immunosuppressive treatment should be initiated if irAEs cannot be controlled by corticosteroids. 				
Immune-related AEs	Toxicity grade or conditions (CTCAEv4.0)	Action taken to pembrolizumab	irAE management with corticosteroid and/or other therapies	Monitor and follow-up
Pneumonitis	Grade 2	Withhold	Administer corticosteroids (initial dose of 1-2 mg/kg prednisone or equivalent) followed by taper	
 • Monitor participants for signs and symptoms of pneumonitis • Evaluate participants with suspected pneumonitis with radiographic imaging and initiate corticosteroid treatment • Add prophylactic antibiotics for opportunistic infections
	Grade 3 or 4, or recurrent Grade 2	Permanently discontinue		

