7: Hematology: Hemoglobin, Absolute Neutrophils Count (ANC), Platelets. Blood chemistry: creatinine, AST, ALT, alkaline phosphatase, total bilirubin, glucose, TSH. There is no need to repeat hematology and blood chemistry prior to the first dose of study treatment, provided that they were done at screening within 7 days prior to randomization, unless deemed clinically required by the Investigator. During treatment period: In Arm A, hematology will be done within 3 days of every visit prior to each CC-486 cycle and on Days 8, 15 and 22 (\pm 1 day). Blood chemistry will be done within 3 days of every visit prior to each CC-486 cycle. There is no need to repeat them prior to pembrolizumab administration unless clinically indicated and/or required according to the standard of care at the institution. In Arm B, hematology and blood chemistry will be done within 3 days of every visit prior to each pembrolizumab infusion.

8: There is no need to repeat CA-125 prior to first dose of study treatment provided that it was done at screening within 7 days of enrollment. Whenever possible, CA-125 should be tested at the same laboratory and with the same technique throughout the study. At the End of Treatment visit and during the follow-up, CA-125 will only be tested in subjects without irPD at time of study treatment discontinuation.

9: During the follow-up phase, only AEs and SAEs related to study treatments that are ongoing by the End of Treatment visit are to be reported and/or followed up (refer to section 6.3.4).

10: Concomitant treatments to be collected from date the PDCF is signed

11: Only concomitant treatments to treat AEs/SAEs related to study treatment will be recorded after the End of Treatment visit

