6.3.4.2 Part B

All subjects will be followed-up.

Subjects discontinued from study treatment for reasons different than progressive disease per irRECIST (e.g. unacceptable toxicity, Investigator's decision, etc.) will be followed up to assess response/progression (with tumor burden assessments and CA-125) every 12 weeks (± 1 week) until irPD.

Once irPD is declared, all subjects will be followed for survival every 6 months (through visit or phone contact) until death or for at least 1 year after the End of Treatment visit, to assess the survival status.

Any AE or SAE related to study treatments that is ongoing by the End of Treatment visit, must be followed up to resolution or until the events have resolved (or return to baseline) or in the Investigator's opinion, are unlikely to resolve due to the nature of the condition and/or the subject's underlying disease.

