7. SAFETY MONITORING

7.1 Definitions

7.1.1 Period of Observation

At each visit and any contact during the study and follow-up period, the Investigator or designee will inquire about the occurrence of AEs and will document them in the subject file.

The Investigator or designee will report the AEs in the eCRF and to TRIO Drug Safety and Pharmacovigilance Department when required as per the table below:

Table 8: Reporting period of AEs/SAEs

Study period	AEs (non-serious)		Serious Adverse Events/Pembrolizumab Events of Clinical Interest (ECI)	
	Part A	Part B	Part A	Part B
From PICF to first dose	Not required to report	Only if related to study participation	Only if related to study participation	Only if related to study participation
Study treatment period until End of Treatment visit	All (regardless of relationship)	All (regardless of relationship)	All (regardless of relationship)	All (regardless of relationship)
From End of Treatment visit until End of subject participation ¹	Only if related to study treatment	Only if related to study treatment)	All (regardless of relationship)	Only if related to study treatment

¹ The applicable events as per the table that are ongoing at time of the End of Treatment visit should be followed up to resolution or until the event becomes stable (or returns to baseline) or is unlikely to resolve further in the opinion of the Investigator. Regarding SAEs, in Part A all should be reported/ followed after the End of Treatment visit, regardless of the relationship with the study drugs. In Part B, only study-drug related SAEs should be followed/ reported.

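### Part B: Table 7 footnote 9 restricts post-treatment reporting to related events already ongoing at End of Treatment, while Table 8 asks for related events whenever they start

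*Protocol*

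**What the plan says.** Footnote 9 to the Part B schedule (Protocol 6.2.2, Table 7) governs AE assessment once treatment has ended. Its rule reads: "only AEs and SAEs related to study treatments that are ongoing by the End of Treatment visit are to be reported". The footnote puts the same limit on which events are followed, and it sends the reader to section 6.3.4.

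Table 8 (Protocol 7.1.1) sets reporting by study period. Its last row is headed "From End of Treatment visit until End of subject participation". In the Part B columns, for non-serious AEs and for SAEs and events of clinical interest alike, the entry is "Only if related to study treatment". The note under the table says that the applicable events "that are ongoing at time of the End of Treatment visit should be followed up to resolution" (or until stable or unlikely to resolve further), and closes with: "In Part B, only study-drug related SAEs should be followed/ reported".

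Section 6.3.4.2, the Part B part of the section that footnote 9 cites, opens its AE sentence with "Any AE or SAE related to study treatments that is ongoing by the End of Treatment visit" and requires such events to be followed until they resolve or are judged unlikely to.

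On timing, 5.7.2.2 says of events associated with pembrolizumab: "These adverse events may occur shortly after the first dose or several months after the last dose of treatment". Section 5.7.2.3 adds that immune-mediated reactions can arise once treatment has been discontinued.

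**The concern.** The two Part B rules differ on one class of event: a treatment-related AE or SAE whose onset is after the End of Treatment visit. Table 8 wants it reported and footnote 9 excludes it. With an immune checkpoint inhibitor this class matters, because the protocol itself expects some reactions to begin after dosing has ended.

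Two things depend on the answer. The first is safety oversight: the sponsor can assess a suspected unexpected serious reaction (7.1.3.3, 7.5) only if the site sends it in. The second is the Part B safety data: safety and tolerability of the combination is a secondary objective (2.2.2), and the analysis one year after the primary analysis includes safety (8.8). If some sites apply Table 8 and others footnote 9, late events will be collected unevenly, and a low count could reflect either few events or little reporting.

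**Working it through.** No statistical figure is involved, so the check sets the passages side by side.

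**1. Do the rules differ?** Take a related SAE in Part B that starts after the End of Treatment visit.

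| Source | Condition for reporting | Is this event reportable? |
|---|---|---|
| Table 8, last row, Part B | Related | Yes |
| Note under Table 8, Part B SAEs | Related to study drug | Yes |
| Table 7 footnote 9 | Related and ongoing by End of Treatment | No |
| 6.3.4.2 | None stated; covers only follow-up of ongoing events | Silent |

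A related non-serious AE gives the same result in every row except the second, which concerns SAEs only.

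**2. Could footnote 9 be a rule about follow-up only?** No. It names reporting as well as follow-up. The note under Table 8 separates the two: the row entries decide what is reported, and being ongoing at End of Treatment decides what is followed to resolution. Footnote 9 merges them.

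**3. Does another section settle it?**
- 6.4.4 sends the reader, for AE assessment and collection, to section 7 and to the schedule in 6.2. These are the two conflicting sources, and no order of precedence is given.
- 6.2 requires adherence to the schedule, so a site applying footnote 9 can say it is complying.
- The SAP covers Part A only and leaves Part B to separate documents.

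**4. Does the restriction look deliberate?** The surrounding text suggests not.
- The matching Part A footnote (Table 6, footnote 9) has no ongoing condition.
- Table 8 has separate Part B columns. For SAEs after End of Treatment they narrow the Part A rule to related events, with no narrowing by onset.
- Table 7 footnote 11 and 6.4.4 record treatments given for related AEs or SAEs after End of Treatment, again without an ongoing condition. Under footnote 9 a site could record a drug given for an event that it is told not to report.

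**5. When does the gap open and close?** The End of Treatment visit is 30 ± 7 days after the last administration of any study drug (Table 7 footnote 3): 30 − 7 = 23 and 30 + 7 = 37, so day 23 to day 37. The disputed period starts there. Under 6.3.4.2, subjects are then followed for survival, once progression is declared, until death or for at least one year after that visit. This period includes the months in which 5.7.2.2 says events may still appear.

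**The case against.** The strongest reply is that section 7 is the dedicated safety section, that it is clear, and that it has back-ups. Section 7.1.1 already requires investigators to ask about AEs at every visit and contact, follow-up included, and to document them in the subject file. The note under Table 8 repeats the Part B rule for related SAEs with no onset limit. Section 7.1.4 ties events of clinical interest to the collection period in 7.1.1, and footnote 9 does not mention them. Section 9.3 separately obliges the investigator to report serious events to the ethics committee and inform the sponsor. A site working from section 7 would report a late related event.

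Most of this stands, and it limits the consequence. It does not remove the conflict: enquiry and a note in the subject file do not decide what is sent to the sponsor, and that is where the two rules disagree. Section 9.3 concerns serious events, so it does not help with non-serious ones.

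Stronger readings are tempting, and the documents do not support them:
- **That late immune toxicity will be lost.** This holds only at sites that apply footnote 9 over section 7, and nothing shows how many would.
- **That 6.3.4.2 is a second contradiction.** It sets a duty to follow ongoing related events, which agrees with the note under Table 8. It does not limit reporting.
- **That footnote 11 needs correcting.** It already agrees with Table 8.
- **That every subject is exposed for at least 12 months.** The follow-up rule ends at death if that comes first, and the protocol (1.1) gives a median overall survival of about 12 months for platinum-resistant disease at first relapse. Some subjects can be expected to die before a full year after the visit.

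**Conclusion.** Footnote 9 is wrong as written. It contradicts Table 8 on whether related AEs and SAEs starting after End of Treatment are reported in Part B, and no provision says which prevails. A site that follows it could, while complying with the schedule, leave a new late related event unreported to the sponsor.

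The exposure runs from the End of Treatment visit until death or at least one year later, for at most the 150 subjects planned for Part B. The documents give no rate for late related events, so the number at risk of going unreported cannot be estimated. The conclusion rests on reading the footnote as it stands. It assumes nothing about how often sites would prefer it to section 7.

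**What to change.** Reconcile Table 7 footnote 9 with Table 8. Reword the footnote so that in Part B follow-up, related AEs and SAEs that start or are ongoing after the End of Treatment visit are reported. Keep the ongoing condition only for which events are followed to resolution, and refer to section 7.1.1 for the full rule. Section 6.3.4.2 needs at most a cross-reference to Table 8. Footnote 11 needs no change, and the duty to enquire at each contact is already in 7.1.1.

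The cost is one reworded footnote and, optionally, one cross-reference, with no new visits, tests or analyses. Section 3.2 already allows a protocol amendment before Part B, which would be a convenient place for it.

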6.3 Study Visits and Assessments/Investigations

During all visits below, assessments should be done according to the Schedule of Visits and Assessments (section 6.2). The description/details of the different assessments are found in section 6.4.

6.3.1 Baseline/Screening Period

The baseline/screening period starts with the signature of the PICF and ends when the subject is enrolled in Part A, randomized in Part B or screen failed.

During the screening period the following assessments will be done:

- Demographics, Medical History
- Complete physical examination (including weight)
- Vital signs (according to standard of care)
- ECOG PS
- Laboratory assessments:
 - Hematology: Hemoglobin, Absolute Neutrophils Count (ANC) and Platelets
 - Blood chemistry: creatinine, AST, ALT, alkaline phosphatase, total bilirubin, glucose, TSH
 - Coagulation tests: INR or PT and aPTT/PTT
 - Serum pregnancy test: only in women of childbearing potential (within 7 days of registration)
 - CA-125

Notes: If for some reason laboratory tests are repeated between these tests done at screening and treatment start, the most recent measurement obtained prior to treatment start must be within the required values according to the inclusion criteria, to begin study treatment.

- Adverse events assessment
- Concomitant medication
- Tumor burden assessments
- Tumor biopsy
- Collection of FFPE block from debulking surgery (optional)

6.3.2 Treatment Period Visits

Study treatment should begin within 3 days of enrollment in Part A or randomization in Part B. All assessments should be performed within 3 days of the scheduled visit, unless otherwise specified. All pre-treatment tests/procedures should be performed and assessed by the Investigator prior to dosing.

During the treatment period, visits will be done as follows:

6.3.2.1 Part A

The first on-treatment visit should occur on Day 1 of the 1st CC-486 cycle (subject should receive the first CC-486 dose during the visit and after the whole blood sample for DNA methylation was drawn as per section 5.3.3.2). Afterwards, visits will be done every 4 weeks \pm 3 days, during the CC-486 off period as close as possible to restarting the subsequent CC-486 cycle.

During the treatment period visits the following assessments will be done:

- Physical examination (symptom-oriented)
- ECOG PS
- Adverse events assessment
- Concomitant medication
- Laboratory assessments:
 - Hematology: Hemoglobin, Absolute Neutrophils Count (ANC) and Platelets
 - Blood chemistry: creatinine, AST, ALT, alkaline phosphatase, total bilirubin, glucose, TSH
 - Coagulation tests and pregnancy test: only if clinically indicated
 - CA-125
- Tumor burden assessments: if applicable according to sections 6.2 and 6.4.6.1
- Tumor biopsy: if applicable according to sections 6.2 and 6.4.7.1.
- Whole blood sample for DNA methylation analysis: if applicable according to sections 6.2 and 6.4.7.3

Prior to the first CC-486 cycle, there is no need to repeat hematology, blood chemistry and CA-125 tests provided they were done at screening within 7 days of enrollment, unless deemed clinically required by the Investigator.

In addition to these visits, the subject will visit the clinic at time of each pembrolizumab infusion. There is no need to repeat laboratory tests prior to pembrolizumab administration unless clinically indicated and/or required according to the standard of care at the institution.

Hematology (at least hemoglobin, Absolute Neutrophils Count (ANC) and platelets) will be repeated at day 8, day 15 and day 22 (\pm 1 day) of each cycle. No clinical visit is required on these days. CC-486 dose adjustments, treatment withhold or treatment discontinuation based on hematology test results will be performed as per section 5.7.3.

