- For the treatment of adult and pediatric patients with unresectable or metastatic, microsatellite instability-high or mismatch repair deficient solid tumors who have progressed following prior treatment and who have no satisfactory alternative treatment options, or colorectal cancer that has progressed following treatment with a fluoropyrimidine, oxaliplatin, and irinotecan.
- Patients with recurrent locally advanced or metastatic gastric or GEJ adenocarcinoma whose tumors express PD-L1, with disease progression on or after two or more prior lines of therapy including fluoropyrimidine and platinum-containing chemotherapy and if appropriate, HER2/neu-targeted therapy.

Pembrolizumab is currently being evaluated in clinical trials in several hematologic malignancies and solid tumors.

Pembrolizumab is generally well tolerated and has demonstrated a favorable safety profile in comparison to chemotherapy. The most common treatment related adverse events observed with pembrolizumab are mostly grade 1-2 and include fatigue, diarrhea, decreased appetite, nausea, and anemia. Pembrolizumab is an immunomodulatory agent, and based on this mechanism of action, immune mediated adverse events are of primary concern. Important identified risks for pembrolizumab are of an immune mediate nature, including pneumonitis, colitis, thyroid disorders (hypothyroidism/hyperthyroidism), hepatitis, hypophysitis, Type I diabetes mellitus, uveitis, and nephritis. The majority of immune-mediated adverse events are mild to moderate in severity, are manageable with appropriate care, and rarely require discontinuation of therapy.

Refer to the pembrolizumab Investigator’s Brochure (IB) for additional information on the drug.

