6.1.2.2 Part B

The following steps for registering and randomizing a subject are chronologically performed:

1. The subject must provide written informed consent prior to performing any study specific procedure not considered standard practice by the institution.
2. The site will register the subject in the IWRS system. The registration needs to be done as soon as the subject signs the PICF. The system will uniquely attribute a registration number to each subject in the study and the site will receive an automated registration confirmation.
3. The site will proceed to perform the screening procedures according to the Schedule of Assessments and to sections 6.3 and 6.4. Upon completion of screening procedures the Investigator or his/her delegate will check if the subject meets all eligibility criteria:
 - Subjects who do not meet the eligibility criteria will be moved to a screen failure category in the IWRS.
 - Subjects who meet all eligibility criteria: the sites will enter the screening data in the eCRF which will be reviewed centrally by TRIO. After the review of the eligibility criteria, TRIO may address, if necessary, some discrepancies that will have to be answered by the site. Once the eligibility central review is completed and discrepancies have been resolved (if applicable) TRIO will provide the confirmation that the subject is eligible and the site will be able to move forward with the subject's randomization in IWRS. Treatment assignment will be done by the system and the site will receive an automated randomization confirmation.

Subjects will be randomized to treatment arms in a 1:1 ratio. To ensure the equal distribution of prognostic factors in the two study arms, subjects will be stratified according to the following parameters:

- Type of relapsed disease: platinum-refractory vs. platinum-resistant (refer to the corresponding definitions in section 4.1)
- Prior treatment regimens for the platinum-refractory/resistant EOC: none vs. 1 or 2

Details regarding the Registration and Randomization processes are provided in a specific Instruction Manual related to the Registration and Randomization processes.

Subjects randomized in Part B must start study treatment within 3 days of randomization.

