5: There is no window to obtain the signed and dated PICF. Study specific screening assessments not considered standard practice by the institution must start only once the PICF has been signed. Registration takes place as soon as the subject signs the PICF. After screening procedures and if subject meets all eligibility criteria, enrollment will be done according to the process described in section 6.1.2.1.

6: Only in women of childbearing potential. Refer to section 4.1 for definition of women of childbearing potential.

7: Hematology: Hemoglobin, Absolute Neutrophils Count (ANC), Platelets. Blood chemistry: creatinine, AST, ALT, alkaline phosphatase, total bilirubin, glucose, TSH. There is no need to repeat hematology and blood chemistry prior to first dose of study treatment provided that they were done at screening within 7 days of enrollment, unless deemed clinically required by the Investigator. During treatment period hematology will be done within 3 days of every visit prior to each CC-486 cycle and on Days 8, 15 and 22 (\pm 1 day). Blood chemistry will be done within 3 days of every visit prior to each CC-486 cycle. There is no need to repeat them prior to pembrolizumab administration unless clinically indicated and/or required according to the standard of care at the

institution.

8: There is no need to repeat CA-125 prior to first dose of study treatment provided that it was done at screening within 7 days of enrollment. Whenever possible, CA-125 should be tested at the same laboratory and with the same technique throughout the study. At the End of Treatment visit and during the follow-up, CA-125 will only be tested in subjects without irPD at time of study treatment discontinuation.

9: During the follow-up phase, only SAEs (regardless of the relationship to study drugs) and non-serious AEs related to study treatments are to be reported and/or followed up (refer to section 6.3.4).

10: Concomitant treatments to be collected from date the PICF is signed

11: Only concomitant treatments to treat AEs related to study treatment and SAEs (regardless of their relationship) will be recorded after the End of Treatment visit

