6.3.2.2 Part B

In Arm A: The first on-treatment visit should occur on Day 1 of the 1st CC-486 cycle (subject should receive the first CC-486 dose during the visit). Afterwards, visits will be done every 4 weeks \pm 3 days, during the CC-486 off period as close as possible to restarting the subsequent CC-486 cycle.

Additionally the subject will visit the clinic at time of each pembrolizumab infusion.

In Arm B: every 21 days \pm 3 days, prior to each pembrolizumab infusion

During the treatment period visits the following assessments will be done in both arms:

- Physical examination (symptom-oriented)
- ECOG PS

- Adverse events assessment
- Concomitant medication
- Laboratory assessments:
 - Hematology: Hemoglobin, Absolute Neutrophils Count (ANC) and Platelets
 - Blood chemistry: creatinine, AST, ALT, alkaline phosphatase, total bilirubin, glucose, TSH
 - Coagulation tests and pregnancy test: only if clinically indicated
 - CA-125
- Tumor burden assessments: if applicable according to sections 6.2 and 6.4.6.1
- Tumor biopsy (optional): if applicable according to sections 6.2 and 6.4.7.1.

Prior to the first dose of study treatment, there is no need to repeat hematology, blood chemistry and CA-125 tests provided they were done at screening within 7 days of randomization, unless deemed clinically required by the Investigator.

In Arm A, prior to each pembrolizumab infusion, there is no need to repeat laboratory tests unless clinically indicated and/or required according to the standard of care at the institution.

In Arm A only, hematology (hemoglobin, Absolute Neutrophils Count (ANC) and platelets) will be repeated at day 8, day 15 and day 22 (± 1 day) of each cycle. No clinical visit is required per protocol on these days. CC-486 dose adjustments, treatment withhold or treatment discontinuation based on hematology test results will be performed as per section 5.7.3.

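### In Part A and Part B Arm A, required chemistry follows the 28-day CC-486 cycle, so 3 of every 4 pembrolizumab infusions from the second onward can proceed on liver and renal values about 8-22 days old

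*Protocol*

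**What the plan says.** **Chemistry schedule, Part A and Part B Arm A.** Table 6 footnote 7 states: "Blood chemistry will be done within 3 days of every visit prior to each CC-486 cycle". Table 7 footnote 7 sets the same rule for Arm A. The extra draws on Days 8, 15 and 22 of each cycle are hematology only.

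**Waiver before pembrolizumab.** Section 6.3.2.1 puts it as "no need to repeat laboratory tests prior to pembrolizumab administration unless clinically indicated and/or required according to the standard of care at the institution". Section 6.3.2.2 says of Arm A that before every "pembrolizumab infusion, there is no need to repeat laboratory tests unless clinically indicated and/or required according to the standard of care at the institution".

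**Arm B.** Table 7 footnote 7 ties chemistry to the infusion: "In Arm B, hematology and blood chemistry will be done within 3 days of every visit prior to each pembrolizumab infusion". The first dose is an exception in both arms, because repeat testing is waived "prior to the first dose of study treatment, provided that they were done at screening within 7 days prior to randomization".

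**Risk and required action.** Section 1.3.2 lists important identified risks of pembrolizumab that include "hepatitis, hypophysitis, Type I diabetes mellitus, uveitis, and nephritis". Section 5.7.2.2 then says: "Pembrolizumab must be withheld for drug-related toxicities and severe or life-threatening AEs as per Table 1". In Table 1, liver-test elevation suggestive of hepatitis and renal dysfunction each call for withholding at Grade 2 and permanent discontinuation at Grade 3 or 4.

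**The concern.** The Table 1 liver and renal rows depend on laboratory values, yet at most combination-therapy infusions the protocol does not require a current one. A transaminase or creatinine rise may cause no symptoms. Asking about adverse events at each contact (section 7.1.1) would not reveal it, and neither would the clinical-indication exception, which needs something to prompt the test.

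At a site that does no more than the protocol asks, a subject already exposed to pembrolizumab could be re-infused when a change that calls for a hold or stop has not been looked for. The subjects concerned are those on the combination. Section 1.4.2 says no results were publicly available from the two other azacitidine-pembrolizumab studies it mentions.

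This is a safety-monitoring point. It does not touch sample size, power or alpha.

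**Working it through.** The documents give no figure for the age of chemistry at infusion, so there is none to reproduce. The ages follow from the calendar.

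**Inputs**
- CC-486 cycle of 28 days, with the pre-cycle visit every 4 weeks ± 3 days (section 6.3.2.1). Cycle Day 1 falls on study day 1 + 28k: 1, 29, 57, 85, 113, 141.
- First pembrolizumab infusion 7 ± 3 days after CC-486 starts, then every 21 ± 3 days (section 5.2). Infusions fall on day 8 + 21j: 8, 29, 50, 71, 92, 113, 134, 155.
- Chemistry within 3 days of the pre-cycle visit (Table 6 and Table 7, footnote 7).
- Assumption: nominal dates and no treatment delays.

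**Age of the last required panel = infusion day − draw day**

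| Draw relative to cycle Day 1 | Infusion 2 (day 29) | Infusion 3 (day 50) | Infusion 4 (day 71) | Infusion 5 (day 92) |
|---|---|---|---|---|
| Same day | 0 | 21 | 14 | 7 |
| 1 day before | 1 | 22 | 15 | 8 |
| 3 days before | 3 | 24 | 17 | 10 |

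The pattern repeats every 84 days, the least common multiple of 21 and 28, which is four infusions. For each draw day, 3 of every 4 infusions use values more than 3 days old. With the draw one day before, this is 5 of 7 infusions in the first 24 weeks (days 50, 71, 92, 134, 155), and 25 of 34 over infusions 2 to 35.

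**Upper end with windows.** 21 days + 3 (visit window) + 3 (draw window) + 3 (infusion window) = 30 days. All three windows must run the same way, so this is a permitted extreme and not a typical value.

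**How many such infusions before the next check.** With draws on days 28, 56, 84 and 112:
- days 28-56: infusions on day 29 (current values) and day 50 (older values);
- days 56-84: day 71 (older);
- days 84-112: day 92 (older).

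So at most one infusion on older values falls between consecutive required panels.

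**First infusion.** In Part A and Arm A, screening chemistry may be 7 days before enrollment or randomization, treatment starts up to 3 days after it, and the infusion follows 7 days later: 7 + 3 + 7 = 17 days, or 20 with the +3-day infusion window. The 3-day start rule for Part B is explicit: "Subjects randomized in Part B must start study treatment within 3 days of randomization". In Arm B the first infusion is the first dose, so its limit is 7 + 3 = 10 days.

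**Scheduled panels per 84 days.** Arm A now: 84/28 = 3. Arm B: 84/21 = 4. With chemistry also required before each infusion, Arm A would have 3 pre-cycle draws + 4 pre-infusion draws − 1 that coincides = 6.

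**The case against.** The waiver is deliberate. It appears in two footnotes and two sections, each time with exceptions for clinical indication and site standard of care. Table 1 says what to do once a toxicity is found and sets no testing interval. A reader might infer that the schedule contradicts Table 1; it does not, because both can be followed as written. What is missing is a requirement for the test that would show whether a hold is due.

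Section 5.7.2.2 also sends investigators to the Investigator's Brochure for assessing and managing immune-related events. The Brochure is not available here and may ask for more testing. Together with site practice, this may close the gap at some sites, but the protocol itself does not require it.

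Nor does every abnormal value trigger a hold. The rule covers drug-related toxicities and severe or life-threatening events, and the liver row requires a pattern suggestive of hepatitis. Section 1.3.2 adds that most immune-mediated events are mild to moderate and rarely lead to discontinuation. These points limit the consequence. They do not remove the need for a current value to judge whether the rule applies.

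Two general statements might seem to fill the gap. The synopsis calls for safety assessments at each visit but defers to the schedule tables. Section 6.3.2 requires pre-treatment tests to be assessed before dosing, but this cannot restore a test that the specific text waives.

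Finally, 3 of 4 might be read as a run of unmonitored doses. The calendar shows otherwise: a required panel separates each such infusion from the next.

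**Conclusion.** The point holds as a gap in the protocol minimum. In Part A and Part B Arm A, 3 of every 4 infusions from the second onward can proceed on liver and renal values 8-22 days old. The range is 7-21 or 10-24 days with other draw days, and up to about 30 days if all windows add up. The first infusion can rest on screening values up to about 17-20 days old. Arm B, on pembrolizumab alone, has chemistry within 3 days of each pre-infusion visit after the first dose, so the protocol already treats testing tied to each infusion as feasible.

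The figures assume nominal dates, no delays and a site that tests no more than required. On that calendar the exposure is one infusion on older values per interval between required panels. The documents do not say how many sites rely on the minimum or how often a symptom-free rise occurs. They therefore do not support any claim that subjects will be harmed at a given rate, or that combination subjects generally go unmonitored. A cheap improvement is warranted.

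**What to change.** In Table 6 footnote 7, Table 7 footnote 7, and sections 6.3.2.1 and 6.3.2.2, replace the chemistry waiver with:

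*In Part A and Arm A, at least creatinine, AST, ALT, alkaline phosphatase, total bilirubin and glucose will be done within 3 days before each pembrolizumab infusion from the second onward and reviewed before dosing; one draw serves both purposes when it coincides with the pre-cycle chemistry.*

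Alkaline phosphatase is needed because the hepatic event of clinical interest in section 7.1.4 uses it together with AST/ALT and bilirubin. Keep the pre-cycle chemistry, since the CC-486 renal rule in Table 5 relies on creatinine. The first infusion can stay as it is, because no pembrolizumab has yet been given. The hematology schedule and Table 1 do not change.

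**Cost.** An amendment to two footnotes and two paragraphs. About 2 extra panels per subject in the first 12 weeks (days 50 and 71), then 3 per 12 weeks (days 92, 134 and 155 in the second period). On the nominal calendar these fall on cycle Days 22, 15 and 8, when hematology is drawn anyway and the subject attends for infusion. There is added laboratory and data-entry work and a possible wait for results before dosing.

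**Side effect on the comparison.** Scheduled panels per 84 days go from 3 versus 4 (Arm A versus Arm B) to 6 versus 4. More frequent testing gives more chances to record a high grade, so the by-arm laboratory summaries in protocol section 8.6, worst-grade tables above all, must be read with that difference stated. The current SAP covers Part A only; the note belongs in the separate Part B analysis document.
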